#### 4.3 Toxicity Management & Dose Delays/Modifications

Any patient who receives at least one dose of study therapy will be evaluable for toxicity endpoints. Each patient will be assessed for the development of toxicity according to the timeframe referenced in the Schedule of Events table (section 5). Toxicity will be assessed according to CTCAE v5.0.

- In order to start a new cycle of therapy a patient must have platelets  $\geq$  100,000, ANC  $\geq$  1,000, and resolution of all treatment-related toxicity (except alopecia) to Grade 2 or less or to baseline when baseline was more than Grade 2.
- A dose can be delayed for up to 7 days for resolution of toxicity. The subsequent doses will be delayed so as not to shorten the dosing interval.
- If the dose cannot be given within 7 days of scheduled time it should be omitted. Patients who miss 3 consecutive doses will be removed from the study.
- Patients will be withdrawn from the study if they fail to recover to CTCAE 5.0  $\leq$  1 or baseline from a drug-related toxicity (except alopecia)  $\leq$  4 weeks.
- Patients can have a maximum of 2 dose reductions for drug-related toxicity beyond which they will be removed from the study. Dose reduction should follow the dose levels displayed in the table below. Re-escalation is not permitted.

Dose modifications

Dose Level	Dose of sEphB4-HSA
Starting Dose	1000mg IV over 60 min every 2 weeks
-1	750 mg IV over 60 min every 2 weeks
-2	500 mg IV over 60 min every 2 weeks

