##### 4.3.1 Dose modifications for sEphB4-HSA treatment related toxicity

Toxicity	Grade	sEphB4-HSA
Non-hematologic toxicities including nausea, vomiting , and diarrhea	Grade 1/2	If patients develop intolerable Grade 1 or Grade 2 toxicities (per patient) then they can undergo a dose reduction. For Grade 3/4 toxicities despite optimal medical therapy, hold sEphB4-HSA until equal or under Grade 1. Resume at one dose level reduction.  No routine prophylactic anti-emetic treatment is required at the start of study treatment, however, patients should receive appropriate anti-emetic treatment at the first onset of nausea or vomiting and as required thereafter, in accordance with local treatment practice guidelines
General non-hematologic toxicities excluding nausea,	Grade 3/4	Any patient who experiences Grade 3 or 4 unmanageable non-hematologic toxicity (other than alopecia) at least possibly related to the study

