## NU Study Number: NU 18U10

vomiting, and diarrhea		drug will require immediate dose interruption. Treatment will be withheld until toxicities have resolved to Grade 1 or baseline. After resolution of the toxicity, a one dose level reduction will be initiated.
AST/ALT	Grade 3	Grade 3 AST and/or ALT that does not represent at least a two grade increase from baseline – hold therapy, recheck weekly. If AST and ALT return to baseline grade within 7 days, retreat at same dose level. If AST and ALT do not return to baseline within 7 days, treatment should be restarted once AST and ALT have returned to baseline and dose should be reduced by one level.  Grade 3 AST and/or ALT that represents at least a two grade increase from baseline or $AST/ALT \geq 10 \times UNL$ –hold therapy, recheck weekly, initiate retreatment when resolved to baseline with one dose level reduction.
	Grade 4	Grade 4 AST and/or ALT– hold therapy, recheck weekly, initiate retreatment when resolved to baseline with a one level dose reduction.  Any grade AST or ALT that represents a doubling from baseline AND that is concurrent with a doubling of the total bilirubin- hold therapy, recheck weekly, initiate retreatment when resolved to baseline grade or grade 1 with one level dose reduction.
	Grade 2	Patients with grade 2 hypertension as evidenced by two or more different measurements that are at least one our apart should be initiated on antihypertensive therapy per the treating physician. BP should be rechecked in one week after initiation of antihypertensive therapy; if SBP is still $>150$ and/or DBP is $> 100$ , physician should increase the dose of the antihypertensive or add a second antihypertensive drug as indicated.
Hypertension 	Grade 3	First occurrence, patients may continue on treatment while their antihypertensive therapy is optimized. A second occurrence of grade 3 hypertension despite antihypertensive therapy would require holding treatment with sEphB4-HSA until hypertension returns to $\leq$ grade 2 at which point treatment can be resumed with one dose reduction.
	Grade 4	Withhold study drug. Optimal management with intensive IV support in ICU.
Platelets	Grade 3/4	Hold therapy, recheck weekly, initiate retreatment when resolved to Grade 1 or less and restart treatment with a one level dose reduction.

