Neutropenia	Neutropenic fever or Grade 4 neutropenia	Hold therapy, recheck weekly, initiate retreatment when resolved to Grade 1 or less and restart treatment with a one level dose reduction.
Anemia	Grade 1 or Grade 2 (Hemoglobin (Hb) $> 8$ g/dl)	Investigate and manage as deemed appropriate by the investigator with or without interruption of study drug or change in dose, taking into account previous history of anemia. Common treatable causes of anemia (e.g., iron, vitamin B12 or folate deficiencies and hypothyroidism) should be excluded. In some cases management of anemia

NU Study Number: NU 18U10

		may require blood transfusions.
	Grade 3 (Hb < 8g/dl) or worse	
Study treatment should be interrupted for up to maximum of 4 weeks to allow for bone marrow recovery and the patient should be managed appropriately. Study treatment can be restarted at the reduced dose level -1 if Hb has recovered to > 10 g/dl. Any subsequently required anemia related interruptions, considered likely to be dose related, or coexistent with newly developed neutropenia, and or thrombocytopenia, will require a further study treatment dose reduction to level -2.
 
If a patient has been treated for anemia with multiple blood transfusions without study treatment interruptions and becomes blood transfusion dependent as judged by investigator, study treatment should be permanently discontinued.

1. All patients will be educated about the hypertension side effect and instructed to contact the study team if their blood pressure remains under poor control between visits. The patients may be asked to keep a blood pressure log as per treating physician discretion.

*NOTE: Stopping or reducing the dose of study drug can cause a decrease in BP. The treating physician should monitor the patient for hypotension and adjust the number and dose of antihypertensive medication(s) accordingly.*

If the patient experiences a grade 4 allergic or hypersensitivity reaction the drug should be permanently discontinued.

AR targeted therapy will continue per standard of care regardless of sEphB4-HSA toxicity.

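### The Grade 3 anemia rule in 4.3.1 names a fixed restart level (-1, 750 mg) and does not address a patient already at 750 mg for another toxicity

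*Combined protocol and SAP*

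**What the plan says.** Section 4.3 sets three dose levels: 1000 mg to start, level -1 at "750 mg IV over 60 min every 2 weeks", and level -2 at 500 mg. It allows at most two reductions for drug-related toxicity, removes a patient who would need a third, and bars re-escalation.

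In 4.3.1, Grade 3 (Hb below 8 g/dl) or worse anemia leads to an interruption of at most 4 weeks. Then: "Study treatment can be restarted at the reduced dose level -1 if Hb has recovered to" above 10 g/dl. The next sentence deals with later anemia interruptions that are judged probably dose related or come with new neutropenia or thrombocytopenia. Each of these "will require a further study treatment dose reduction to level -2".

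Other rows of the same table put the reduction in relative terms:
- Nausea, vomiting and diarrhea, Grade 3/4: "Resume at one dose level reduction".
- General non-hematologic, Grade 3/4: "After resolution of the toxicity, a one dose level reduction will be initiated".
- Hypertension, second Grade 3 occurrence: "at which point treatment can be resumed with one dose reduction".
- Platelets, Grade 3/4: "initiate retreatment when resolved to Grade 1 or less and restart treatment with a one level dose reduction". The neutropenia row ends the same way.
- AST/ALT, Grade 3 and Grade 4: where a reduction applies, it is one level.

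**The concern.** A fixed level and a one-level step agree only if the patient is still at 1000 mg. A patient can reach 750 mg by another route before any anemia. A second Grade 3 hypertension is one such route, and section 1.5 reports Grade 3 hypertension in 27% of phase I patients, without giving the share who had a second episode. If that patient then has a first Grade 3 anemia, the row offers 750 mg, the dose on which the anemia occurred.

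Two things are at stake. One is dosing after a severe toxicity, where three centers could read the row differently. The other is consistency: the same two toxicities can lead to different doses, and to different counts against the limit of two reductions, depending only on which came first.

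**Working it through.** The plan gives no figure to reproduce. The check sets the rows side by side and applies the dose levels of 4.3.

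**Step 1. Rows of 4.3.1 that state a reduction.** There are eight: nausea/vomiting/diarrhea; general non-hematologic Grade 3/4; AST/ALT Grade 3; AST/ALT Grade 4; hypertension Grade 3; platelets; neutropenia; anemia Grade 3 or worse. Seven are relative to the current dose. Anemia alone names a level.

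**Step 2. First Grade 3 anemia, by current dose.** Change = restart dose / current dose - 1.

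| Current dose | Row read literally | One-level rule |
|---|---|---|
| 1000 mg | 750 mg; 750/1000 - 1 = -25% | 750 mg; -25% |
| 750 mg | 750 mg; 750/750 - 1 = 0% | 500 mg; 500/750 - 1 = -33% |
| 500 mg | 750 mg; 750/500 - 1 = +50%, barred by 4.3 | third reduction, so removal under 4.3 |

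The two rules differ in practice in the second line. In the third, 4.3 overrides the literal reading.

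**Step 3. Does another provision close the gap at 750 mg?**
- The level -2 sentence in the anemia row covers only later anemia interruptions, so it does not reach a first one.
- The limit of two reductions and the re-escalation ban in 4.3 do not require a step down after a hold.
- Section 4.3.2 generally discontinues Grade 4 toxicity. That leaves mainly Grade 3.
- Section 4.5 lets the physician stop for an unacceptable event but requires no reduction.

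**Step 4. Order effect.** This assumes that a restart at an unchanged dose does not count as a reduction, which the text does not state.
- Anemia, then Grade 3 platelets: 1000 to 750 to 500 mg, 2 of 2 reductions used.
- Grade 3 platelets, then anemia: 1000 to 750 to 750 mg, 1 of 2 used.
- Difference: 750 - 500 = 250 mg per infusion.
- A third toxicity that needs a reduction removes the first patient (reduction 3 of 2) and moves the second to 500 mg (reduction 2 of 2).

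**Step 5. How often.** The case needs an earlier reduction for another toxicity, then a first Grade 3 anemia, then Hb above 10 g/dl within 4 weeks, among at most 25 evaluable patients. Section 1.5 does not list anemia among the phase I toxicities and the documents give no anemia rate, so a count cannot be computed. Entry requires Hb of at least 9 g/dL (3.1.9), which is 9 - 8 = 1 g/dL above the Grade 3 cut-off, so Grade 3 anemia itself is not far-fetched.

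**The case against.** The strongest reply is that the row is shorthand for the usual case: the first anemia hold goes to -1 and the next one further down to -2. Calling -1 a reduced level, and the next step a further one, suits a drafter who pictured a patient at 1000 mg. The row can also be read as a ceiling of 750 mg. This stands. A reader might infer that the protocol deliberately prescribes rechallenge at an unchanged dose, and the documents do not support that. They leave one sequence unaddressed.

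A second reply is that an unchanged dose after a Grade 3 event is not peculiar to anemia. Grade 3 AST/ALT less than two grades above baseline that settles within 7 days is retreated at the same dose, and a first Grade 3 hypertension may continue on treatment. This also stands. Resuming the same dose is therefore not in itself out of line with the table. The difference is that those rows state the outcome, while the anemia row speaks of a reduced level that, for this patient, reduces nothing.

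Third, there are safeguards. Restart needs Hb above 10 g/dl, stricter than the entry threshold of 9 g/dL. The hold is limited to 4 weeks, and 4.3 withdraws patients who do not recover from a drug-related toxicity in that time. A later anemia interruption that meets the row's conditions forces level -2, and the investigator may dose lower or stop. These limit the exposure, in effect, to a further trial of 750 mg after recovery, but none requires a reduction at that restart. The freedom in the Grade 1/2 row, "with or without interruption of study drug or change in dose", does not govern Grade 3 and adds nothing either way.

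Last, a mandatory step is not free of harm. With no dose-related anemia signal in the documents, it uses up a reduction sooner. That is a fair cost and is counted under the fix.

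**Conclusion.** The gap is real and minor. Read literally, a patient already at 750 mg for another toxicity may resume 750 mg after a first Grade 3 anemia hold with no reduction required, where the table's usual one-level step would give 500 mg. The same pair of toxicities can leave two patients 250 mg apart.

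This rests on the literal reading of level -1 as a dose to restart at. The contrast in removal also rests on not counting an unchanged-dose restart as a reduction. The number of patients affected is unknown and probably small.

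Two stronger readings should be set aside. The row does not raise a 500 mg patient to 750 mg, because 4.3 bars re-escalation; at level -2 the wording is only awkward. Nor does the point touch the two-stage design: no sample size, error rate or analysis figure changes.

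**What to change.** Reword the Grade 3 anemia cell in 4.3.1 in two places:
- Restart: one dose level below the current dose once Hb exceeds 10 g/dl; if the patient is already at level -2, discontinue under 4.3.
- Later anemia interruptions: replace the named level -2 with one further dose level, and keep the existing conditions on dose-relatedness or new cytopenias.

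A patient at 1000 mg still restarts at 750 mg, as now. The change is one table cell in an amendment, with no added assessments and no change to the statistics. The clinical cost should be stated in the amendment: a patient already at 750 mg uses the second of two permitted reductions at the anemia restart, so a later toxicity that needs a reduction would remove that patient sooner than under the literal text.

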#### **4.4 Concomitant Medications/Treatments**

Required premedications are described in Table 4-2-1. There are no other known concomitant medications or treatments associated or recommended with sEphB4-HSA at this time.

In the absence of treatment delays due to adverse event(s), concurrent therapy for prostate cancer with the exception of ongoing androgen deprivation and anti-resorptive agents such as bisphosphonates or denosumab are not permitted. If a patient develops a single symptomatic or imminently dangerous metastasis (such as fracture or vertebral compression) then intervention with radiation therapy and/or surgery is permitted after discussion with the study PI. In this case, study drug would be held during the intervention and recommenced after

**NU Study Number:** NU 18U10

completion and recovery from any adverse effects. The hold on study drug should not exceed 4 weeks.

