**6.1.5 PSA response criteria:**

These definitions are intended to characterize the PSA changes on study for the purpose of reporting of results.

Complete Response (CR): Undetectable PSA ( $\leq 0.2$  ng/ml) that is confirmed by another PSA level at no less than 4 weeks interval ( $\pm 3$  days).

Partial Response (PR): Decrease in PSA value by  $\geq 50\%$  that is confirmed by another PSA level at no less than 4 weeks interval ( $\pm 3$  days).

Stabilization (SD): Patients who do not meet the criteria for PR or PD for at least 90 days on study will be considered stable

Progression (PD): 25% increase over baseline or nadir whichever is lower and an increase in the absolute value of PSA level by 2 ng/ml that is confirmed by another PSA level at no less than 4 weeks interval.

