### 9.1 Description of Correlative studies:

#### 9.1.1 The role of EpHB4 in driving mCRPC

Abundant evidence from human and transgenic mouse studies indicate that alterations in key cancer genes, including MYC, an oncogene and PTEN, a tumor suppressor and negative regulator of PI3K activity can conspire to lead to aggressive prostate cancer [23]. EphB4 supports cMYC expression at transcriptional level in

colon cancer [25]. Further, kinomic analyses of EphB4 mutations in lung cancer revealed the involvement of PTEN or TP53 loss, and activation of EGFR or IGF1R pathways [26]. EphB4 can promote tumorigenesis by engaging multiple signaling pathways, including the PI3 kinase/AKT pathway [27]. We are particularly interested in determining if sEphB4-HSA treatment modulates PI3K/AKT pathways in Myc driven tumorigenesis. For this, we will evaluate the expression of MYC, PI3K and downstream mediators pS6K.

In addition to PI3K pathways, preliminary studies from [name] and [name] laboratories show that the expression of EphB4 level is retained after Androgen Deprivation Therapy (ADT), indicating that it can be a target in cancers after ADT. We also want to explore if sEphB4-HSA cooperates with enzalutamide or abiraterone. There is an interesting relationship between the PI3K and AR pathways in castration-resistant prostate cancer with therapeutic implications. Combining AR inhibition with PI3K inhibition may be an effective strategy for treating Pten-null CRPC [28]. As shown in the preliminary results, sEphB4 treatment inhibits that PI3K pathway, thereby providing a rationale for combining sEphB4 with AR pathway inhibition. We will evaluate the expression of AR in primary and metastatic tissue of patient and correlate the status of AR as a predictive biomarker for response to sEphB4-HSA treatment.

Mechanistically, sEphB4-HSA acts by binding to Ephrin B2 and preventing its binding to EphB4. Given the cooperation between Ephrin B2 expressing endothelial cells and EphB4 expressing tumor cells [29], it is important to investigate the expression of both molecules in this treatment setting. To this end, we will evaluate the expression of EphB4 and Ephrin B2 in the tumor microenvironment of patient tissue and correlate to treatment response.

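### PSA complete response is defined by level alone, so a patient entering with PSA below 0.4 ng/mL could count as a responder without a 50% fall

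*Combined protocol and SAP*

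**What the plan says.** Section 6.2 makes the primary endpoint the proportion of treated patients with a PSA partial or complete response, and takes both definitions from 6.1.5. There, partial response is a fall of at least 50%. Complete response is a level: "Complete Response (CR): Undetectable PSA", set at 0.2 ng/mL or below. Both need confirmation by a second PSA at least 4 weeks later (±3 days). The complete-response line mentions no baseline and no fall. The section opens by saying: "These definitions are intended to characterize the PSA changes on study for the purpose of reporting of results".

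Section 3.1.5 asks for progression on any one of three criteria. The 2.0 ng/mL minimum belongs to the PSA criterion. The soft-tissue and bone criteria carry no PSA minimum.

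On concurrent treatment, the closing notes of 4.3.1 state: "AR targeted therapy will continue per standard of care regardless of sEphB4-HSA toxicity". Section 4.4 instead bars everything beyond ADT and anti-resorptives, under a condition: "In the absence of treatment delays due to adverse event(s), concurrent therapy for prostate cancer with the exception of ongoing androgen deprivation". For a single symptomatic or dangerous metastasis, 4.4 adds that "intervention with radiation therapy and/or surgery is permitted after discussion with the study PI", after which study drug restarts: "The hold on study drug should not exceed 4 weeks".

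**The concern.** In a single-arm trial every counted response is credited to the drug. The complete-response rule can be met by a patient whose PSA did not change, or fell by less than half. The decision turns on small counts (2 of 15 to continue, 6 of 25 for success), so one such patient can matter when the drug's own rate is close to the 10% null.

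The treatment wording raises a lesser worry. If a site took 4.3.1 literally, or read the ban in 4.4 as lifted during a toxicity delay, a PSA fall could be due to another agent. PSA values after on-study radiotherapy or surgery raise the same question of attribution, because neither 6.1.5 nor 6.2 says how to treat them.

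**Working it through.** **1. Who falls in the gap.** Let B be baseline PSA, with a confirmed on-study value of 0.2 or below.

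- The fall is at least (B − 0.2)/B. It is guaranteed to reach 50% when B − 0.2 ≥ 0.5B, that is, when B ≥ 0.4 ng/mL. Such a patient also meets partial response, so the missing condition has no effect.
- If B = 0.3 and PSA becomes 0.2, the fall is 0.1/0.3 = 33%. This is a complete response but not a partial response.
- If B ≤ 0.2 and PSA stays there, the fall can be zero. PSA is drawn on Day 1 of Cycles 3 and 5, which are 28 days apart, so this patient would be a confirmed complete response by Cycle 5. After 90 days the same patient also fits the 6.1.5 definition of stabilization, which requires only that partial response and progression are absent.

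The gap is therefore confined to B < 0.4 ng/mL. Entry under the PSA criterion is excluded from it by the 2.0 minimum; entry on imaging alone is not.

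**2. The plan's own figures.** Inputs from 10.1: 15 + 10 patients, continue with 2 or more responses, success with 6 or more, p0 = 0.10, p1 = 0.30. With X1 ~ Bin(15, p) and X2 ~ Bin(10, p):

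P(success) = Σ over x ≥ 2 of P(X1 = x) · P(X2 ≥ 6 − x)

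At p = 0.10 the terms are 0.0034 (x = 2), 0.0090 (3), 0.0113 (4), 0.0068 (5) and 0.0022 (6 or more), which sum to 0.0328 before rounding. Early stopping is 0.2059 + 0.3432 = 0.549, and the average sample size is 15 + 0.451 × 10 = 19.51. At p = 0.30, P(success) = 0.8017, so beta = 0.198. All agree with the table in 10.1.

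**3. Sensitivity to one certain false responder.** This is an assumption, since the documents give no frequency. If the false responder is in stage 1, the other patients are 14 + 10, and success needs at least 1 true response among the 14 and at least 5 in all:

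P = Σ over x ≥ 1 of P(Bin(14, p) = x) · P(Bin(10, p) ≥ 5 − x)

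At p = 0.10 the terms 0.0046, 0.0180, 0.0301, 0.0227 and 0.0092 sum to 0.0847 before rounding. If the false responder is in stage 2, the others are 15 + 9, with at least 2 of 15 still needed to continue.

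| True rate | None | One in stage 1 | One in stage 2 |
|---|---|---|---|
| 10% | 3.3% | 8.5% | 8.2% |
| 8% | 1.2% | 3.8% | 3.7% |
| 5% | 0.1% | 0.6% | 0.6% |

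Setting P = 0.05 and solving for p gives 8.60% (stage 1) and 8.68% (stage 2). Below those true rates, even one certain false responder leaves the chance of a false success under 5%.

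**4. The treatment wording, set side by side.** In 3.1.4 AR targeted therapy means abiraterone, enzalutamide and newer antiandrogens, on which patients must already have progressed. Section 3.2.3 requires other systemic therapy to be stopped before entry and ADT to continue. Section 4.1 gives ADT as the only background treatment. The hormonal treatment a patient can be continuing is therefore ADT. The conditional opening of 4.4 leaves only a short window: "If the dose cannot be given within 7 days of scheduled time it should be omitted", and 4.5 ends treatment at a delay of 4 weeks or more. Nothing authorises another agent in that window.

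**The case against.** **A fall was clearly meant.** The opening of 6.1.5 speaks of changes, and 6.2 of achieving a post-treatment response. This is good evidence of intent, but general phrases do not override an explicit numerical definition that 6.2 adopts. The Study Summary also cites PCWG3 for the endpoint. That source is not available here, and 6.2 points to 6.1.5.

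**The case is very narrow.** This stands. It needs a baseline below 0.4 ng/mL in a patient with progressive metastatic disease after an AR agent. It limits the size of the problem but does not close the gap.

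**Stronger readings a reader might infer.**

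- *The protocol permits enzalutamide or abiraterone on study.* A reader could add that 9.1.1 says "We also want to explore if sEphB4-HSA cooperates with enzalutamide or abiraterone". But 9.1.1 goes on to commit only to measuring AR expression in tissue, and 3.1.4, 3.2.3, 4.1 and 4.4 all point to ADT. This is a slip.
- *PSA values after on-study radiotherapy or surgery must be excluded.* Counting all on-study values under a permitted palliative intervention is a legitimate choice. To mislead under the partial-response rule, treating one lesion would have to cause a confirmed 50% fall, and the documents do not suggest that this is likely. Scoring such patients as non-responders could also use up power that has little slack: losing 1% of true responses at a 30% rate (0.99 × 0.30 = 0.297) takes power from 80.2% to 79.3%.

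**Conclusion.** The point holds as a minor gap in the primary-endpoint definition: complete response lacks a required fall, and entry on imaging progression lacks a PSA floor. It affects only patients with baseline PSA below 0.4 ng/mL.

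A reader might take 8.5% as the trial's type I error rate. The documents do not support that. The figure is conditional on one false responder being certain and on a true rate exactly at the 10% boundary. With no frequency available, no actual inflation is shown. The design's stated operating characteristics are correct. Confidence is high on the wording; no effect on the trial's conclusion is claimed.

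The wording in 4.3.1 and 4.4 is editorial. Handling of PSA after local treatment is optional reporting.

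**What to change.** **Main change, 6.1.5.** Require a fall of at least 50% from baseline for complete as well as partial response, confirmed at 4 weeks or more. Patients who cannot show this stay in the denominator as non-responders. No visits, patients or data are added, since baseline and on-study PSA are already collected. The cost is that a patient entering below 0.4 ng/mL whose PSA becomes undetectable after a smaller fall is not credited. A baseline PSA minimum at entry would address the cause, but it would narrow eligibility.

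**Editorial.** In 4.3.1 replace AR targeted therapy with ADT. In 4.4 delete the opening clause about treatment delays so that the ban is unconditional.

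**Optional.** Leave the primary rule as it is for PSA after on-study radiotherapy or surgery, and report a sensitivity count of the primary endpoint that excludes those values. This has no effect on power and would show any such case.
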